TITLE: Picture This: Learning to Focus and Savor With a Smartphone

NCT: Not yet assigned

DATE: 12/5/25

PICTURE THIS STUDY PROTOCOL

The proposed intervention draws primarily from two paradigms, positive psychology interventions (PPI) and cognitive bias modification (CBI), and marries components of each into a technology-enhanced program designed to increase global well-being and decrease social isolation and depressive symptoms among college students. Although both intervention paradigms are in relatively early stages of investigation, they have garnered an impressive amount of empirical support indicating their success with regard to increasing psychological health. While they have grown out of very different traditions and theoretical cloths, both approaches also aim to uplift individuals who are languishing rather than flourishing and provide behavioral, cognitive, and attentional tools to increase the experience of positive emotion.

Although they come in various forms ranging from the intentional practice of positive thinking to writing letters of gratitude and increasing social interactions, all positive psychology interventions (PPIs) utilize practices, tools, and exercises to cultivate or increase the participant's sense of subjective well-being. They are, by definition, strengths-based and so do not necessarily intend to address deficits or heal pathology; rather, they are designed to optimize, to build, and to elevate. Recently, PPIs have been utilized with participants suffering from depression. While this application may at first blush seem at odds with the definition, a closer look provides clarity. Depression is characterized not only by high levels of negative affect but also low levels of positive affect. Research to date indicates that increased positive emotion in depressed individuals is beneficial with regard to "increased broad-minded coping," (Joiner & Frederickson, 2002), resilience from negative emotions (Tugade & Fredrickson, 2004), and even in preventing relapse (Fava & Ruini, 2003). Accordingly, such interventions are a natural fit for depression. A recent meta-analysis suggests that PPIs are superior to control or comparison groups in enhancing well being and in addressing depressive symptoms; however, PPIs may be relatively more successful for depressed participants and participants who self-select into the interventions (Sin & Lybomirsky, 2009).

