Cognitive models of depression have long posited that individuals suffering from affective disorders (namely, Major Depressive Disorder) show information processing deficits that include increased attention to negatively-valenced cues. For example, when presented with both sad and neutral faces, subjects diagnosed with MDD selectively attended to the sad face, whereas control subjects divided attention between the sad and neutral faces (Gotlib et al., 2004). More recent work indicates that dysphoric individuals lack a protective bias toward positive stimuli (Ellis et al., 2011) and that they have difficulty disengaging from "mood-congruent (i.e., sad, negative)" stimuli (Bradley et al., 1997; Mathews & MacLeod, 2005). There is also some evidence that depressed individuals may be more likely to interpret ambiguous stimuli as threatening. Recently, researchers have tested cognitive bias modification interventions (CBI), which are designed explicitly to modify dysfunctional patterns of information processing including both attentional and interpretation biases. In their meta-analysis of 45 CBM studies, Hallon & Ruscio (2011) found, overall, a medium effect size for the CBMs on cognitive biases and a small, but significant, effect on anxiety and depressive symptoms before the data was corrected for publication bias. Although the effects were no longer significant after correction for publication bias, the authors report a larger and more robust (while still insignificant) effect for CBMs when measured in the context of a stressor, giving credence to the diathesis-stress cognitive paradigm. They also noted that interpretational biases were impacted relatively more than attentional biases by the intervention manipulation, and anxiety symptoms relatively more than depressive symptoms.

Building upon these two disparate bodies of research, the current project aims to test a set of exercises using Smartphones with college and graduate students designed to retrain attention toward moments/events/people that elicit positive emotions, encourage the savoring of such moments, increase social connectedness, and in turn, decrease depressive symptoms. The aims will be achieved by recruiting college/university/graduate students who provide consent to participate in a randomized trial of the intervention and who will be randomly assigned to 1 of 4 conditions.

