- 1) Those participants who are randomized to the active Picture This! savoring condition will be asked to use their Smartphones to take at least two photographs each day for 3 weeks of something that brings them joy or peace and to upload their pictures daily to a drive accessed by study staff (instructions for each condition may be found in Appendix A). Each evening, they will be directed to

complete an online exercise in which they review the photograph(s) taken that day. They are also asked to complete several questions via an internet survey.

- 2) Participants randomized to the Picture This! Plus Social Sharing will do everything as described for the Picture This! group. In addition, each week, they will be directed to share the photos they took during the prior week with a friend or family member (see script provided in Appendix B).
- 3) Those participants who are randomized to the active control condition (Document This!) will also be asked to take 2 photographs each day using a Smartphone and to upload their pictures daily to a drive accessed by study staff. Rather than focusing on and capturing a photo of stimuli that evokes positive emotion, however, they will be directed to take pictures of things in their lives or surroundings that are representative of a “day in the life”. Like the participants in the Picture This! and Picture This! Plus Social Sharing Groups, they will also be asked to complete an online exercise each evening in which they review their documentary photos each evening and also asked to complete a series of questions via an internet survey.
- 4) Finally, participants randomized to the passive control group will NOT be directed to take any pictures during the 3 week intervention period.

All research participants in all 4 groups will be asked to complete a weekly online survey asking about whether they shared the pictures they took as a part of the study or as a part of their regular life (see Appendix F).

At the end of the intervention, all subjects will be provided a list of local mental health resources and will also be provided with the instructions for all 3 picture taking conditions (should they wish to implement any of the other exercises on their own time).

2. Identification of Subjects:

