- 23) **Test of Self Conscious Affect – 3 (TOSCA-3)** is a scenario based measure composed of 16 scenarios of potential positive and negative occurrences in work and social arenas of life. It is designed primarily to assess shame and guilt responses but also includes pride. The respondent is asked to respond to several questions following the scenarios indicating the likelihood of reacting in certain ways. Sixteen of the 32 scenarios are presented at baseline.
- 24) **Irritability Question – One question designed to assess participant irritability at the conclusion of completing the questionnaires was added.**

Following completion of the questionnaire packet and the computerized tasks, the participant will be randomized to 1 of 4 groups. All groups will be provided a packet of instructions to guide their participation in the coming weeks, and the packet will be reviewed with the participant by someone on the research team (see Appendix A). Participants in the 3 picture taking groups will also be provided instructions to create a login to the research drive if they do not have an account and will be provided instructions regarding how to upload their photographs to the research drive.

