In brief, both the Picture This! and the Picture This! Plus Social Sharing groups groups will be asked to utilize their Smartphones to take photographs on a daily basis for 21 days. The participants in the Picture This! and Picture This! Plus Social Sharing Group are asked to notice and then photograph events/situations/people/places/cues that elicit positive emotion (i.e., joy, awe, gratitude). They are asked to take at least two photographs each day. Participants in the active Document This! control group are also asked to take at least two photographs each day for 21 days that they feel is a good representation of their daily lives. The passive control group is not asked to take any pictures over the 21 day period. Each day, participants in the active conditions are asked to upload the photographs taken that day to a Google Drive accessed only by study staff. Participants will not have access to other participants' photographs, only their own. Participants will be informed in the consent form that submission of photographs poses a risk to confidentiality because the photos may include "self-shots" (photos they have taken of themselves) or photos of other things that could be linked back to them personally if by chance the trained and ethically-bound research assistants happen to know the participants.

At the conclusion of the study, participants will be asked in a separate Photo Release Form if they would provide permission to study personnel to use their photographs in research manuscripts, grant proposals, educational presentations, and other media presentations (see Appendix E).

All 4 groups are asked to provide an active email address and instructed to complete a short series of questions nightly that will be emailed to them from our lab email Gmail address. The email will include a link to a survey powered by Google Docs, which includes the MDES, modified to ask participants about feelings experienced during the past 24 hours (see above for description), and 6-9 additional questions designed specifically for this study (see Appendix D for questionnaires designed for both the active and control groups). The 3 active condition groups are also asked to complete a nightly savoring exercise and to answer several questions about the exercise via a link to the exercise sent to their email (see Appendix D).

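### Does giving a savoring exercise to all three active groups put the intervention into the Document This! control arm?

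*Combined protocol and SAP*

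**What the plan says.** The title presents the program as "Learning to Focus and Savor With a Smartphone". The aim, stated before the list of conditions, is a set of exercises "designed to retrain attention toward moments/events/people that elicit positive emotions, encourage the savoring of such moments".

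The list of four conditions opens with "Those participants who are randomized to the active Picture This! savoring condition". Picture This! Plus Social Sharing does all that Picture This! does and adds weekly sharing, so it inherits that description. The third condition, Document This!, is labelled the active control. Its photographs differ in subject: "Rather than focusing on and capturing a photo of stimuli that evokes positive emotion", its participants record everyday life. Its evening task is introduced with "Like the participants in the Picture This! and Picture This! Plus Social Sharing Groups, they will also be asked to complete an online exercise", and the content is to "complete an online exercise each evening in which they review their documentary photos". The fourth condition is a passive control that takes no study photographs.

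Section 3 (Testing Procedure) then says of the nightly tasks: "The 3 active condition groups are also asked to complete a nightly savoring exercise". That sentence refers the reader to Appendix D. The list of conditions refers to Appendix A for each arm's instructions.

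H1, under Hypothesized Outcomes, compares the two Picture This! arms with the active control and with the no-picture control on nine lettered outcomes. Outcome (c) is savoring beliefs. The analysis text after H7 plans contrasts of the experimental conditions with each control condition.

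**The concern.** Savoring is in the title, in the aim and among the H1 outcomes. If the active control also practised it every night for 21 days, a component under test would sit on both sides of the active-control contrast. That contrast could then show what positive rather than documentary photographs add, but not what the savoring exercise adds, and any true difference could shrink.

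Nearby labels make the literal reading harder to dismiss. Section 3 describes Document This! as active. It divides the Appendix D questionnaires between active and control groups, and Document This! fits both descriptions. In the paragraph on reminders it calls all three photograph-taking groups active controls. A reader of the body text alone cannot be sure which nightly task the control receives.

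**Working it through.** **Who is counted.** Four conditions minus one passive control leaves 4 − 1 = 3: Picture This!, Picture This! Plus Social Sharing and Document This!. Section 3 makes the same count when it deals with uploads: "Participants in the 3 picture taking groups will also be provided instructions to create a login". The sentence on the nightly exercise therefore does include the control.

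**Where the word is used.** *Savor* or *savoring* occurs seven times in the supplied text:

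| Place | Uses |
|---|---|
| Title | 1 |
| Statement of aim | 1 |
| Name of condition 1 | 1 |
| Savoring beliefs measure, baseline packet | 1 |
| Nightly exercise, section 3 | 1 |
| Savoring beliefs measure, exit packet | 1 |
| H1 outcome (c) | 1 |

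Only two of the seven attach the word to an arm or to an arm's task: the name of condition 1 and the nightly exercise.

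**The two places side by side.**

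| Arm | List of conditions: evening task | Section 3: nightly exercise |
|---|---|---|
| Picture This! | Online review of the day's photographs; arm named a savoring condition | Savoring exercise |
| Plus Social Sharing | As Picture This! | Savoring exercise |
| Document This! | Online review of documentary photographs, introduced as like the other two arms | Savoring exercise |
| Passive control | None | None |

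The same three arms have a nightly exercise in both columns. In the list of conditions, *savoring* qualifies the name of an arm; no arm's evening task is called savoring there. Because Plus Social Sharing inherits the Picture This! description, the word covers two arms in one place and three in the other. The mismatch is one label on one arm.

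**What the label could change.** H1 has two control comparisons. The passive one is untouched. The active-control one is formed from randomized condition, so its data, model and contrast are the same whatever the exercise is called. Only its interpretation could differ, and only if the delivered content matched the literal label. One of the nine lettered outcomes measures savoring directly.

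**Size, if the literal reading were true.** The plan states no effect size, SD, alpha or allocation ratio, so the following is purely illustrative. Assume equal allocation of the roughly 240 participants (240/4 = 60 per arm), SD 1, two-sided alpha 0.05, and one experimental arm against Document This!. If a shared exercise removed 0%, 25% or 50% of a true difference of 0.5 SD, power would be 0.78, 0.54 or 0.28. For true differences from 0.3 to 0.6 SD the ranges are 0.38–0.91, 0.23–0.69 and 0.13–0.38. The result is driven by the fraction removed, on which the documents are silent. These figures are no evidence that any loss occurs.

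**The case for a change.** The strongest case for a change is that the count leaves no way to exclude the control, and that the name of the intervention's own target is a poor generic name for a control task. A shared savoring exercise and an arm-specific review are both legitimate designs, but they support different conclusions, and the body text does not say which is meant. The exercises go out as emailed links, so loose wording could also lead to the wrong link being sent. A correction would cost a few words.

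Part of this stands. The wording is loose, and so is the reminder paragraph's label for the three groups, although a passage about reminders to take photographs can only mean the groups that take them.

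The step to a design fault does not stand. Staff send links and packets from the appendix materials, not from one adjective in the narrative. A shared photo review would also be a sensible matched control: it holds the nightly task constant and varies the photographs. Nor would a common exercise clearly place the intervention in both arms. The aim concerns savoring moments that elicit positive emotion, and Document This! participants are directed to everyday subjects instead.

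**Conclusion.** No change to the plan follows. This is a labelling slip: the sentence on the nightly exercise uses *savoring* for a photo review that the list of conditions describes in neutral terms for the same three arms. Its reach is at most the interpretation of one of the two H1 control comparisons. The randomized groups, the outcomes, the model and the contrasts stay as they are, and the documents do not show that the control receives savoring training.

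This rests on two assumptions: that Appendices A and D, absent from the supplied text, govern what each arm receives, and that the trial report will describe the delivered exercise by arm. If the exercise proves to be shared, the active-control contrast remains valid as a comparison of positive with documentary photographs under a common nightly task. It should then not be read as isolating the exercise.

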Subjects must freely volunteer to participate. No coercion, implicit or otherwise, is permitted. Describe how potential subjects will be identified and approached (e.g., in class, door to door solicitation, through an ad, etc.). If the contact will be made in person, provide the statement that will be made orally to the potential subject(s). If the contact will be made in writing, submit a copy of the written communication text with this application.

Approximately **240** potential participants will be recruited at Clark University **and at other universities in the larger Worcester community** via flyering around campus as well as around Worcester in off campus public locations, email announcements, in-class announcements, **electronic advertisement boards** and via the Clark psychology subject pool. We would also like to post the contents of the flyers on a Facebook page created for the LEAF lab **as well as [name] website hosted by Clark. In order to extend recruitment beyond Clark, we will attempt to contact officials at other local universities to determine whether they will allow recruitment on their campuses and will follow their guidelines regarding local IRB approval, posting flyers on campus, email blasts, postings on electronic advertisement boards. Upon approval on other campuses, we would use all of the aforementioned resources (flyers on campus, emails, etc.) as appropriate.**

Interested students will be screened for eligibility **either in person or over the phone** (See Appendix C). If eligible, they will be schedule for an appointment, consented, asked to complete a series of questionnaires **and 2 computer tasks**, and then randomly assigned to **1 of 4 groups**.

There is no deceit involved in the study.

3. Testing Procedure:

Outline the testing procedure in sufficient detail to permit the Committee's assessment of potential psychological or physical implications (e.g. length of experiment, possible deception, physical or psychological discomfort). Attach a copy of any questionnaire or written test to be used in the study. For interviews, provide a copy of the interview questions to be used. Some research may be exempted, upon

review, from the IRB. A list of possible exempted research is available on this web page link. If you state that "minimal risk" may occur, please explain why (i.e. subject matter covered, the way responses are gathered, etc.)

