Participants in all 3 active control groups will also be given the opportunity to choose whether they would like to be reminded to take photographs via text message or email. The text messages will be generated from the study Gmail account. Participants are reminded in the consent form that they are responsible for any charges accrued for receiving text messages if they choose that option.

At the end of each 7 day period, participants in the active **Picture This! Plus Social Sharing Group** are asked to share their photographs with a friend, relative, or loved one of their choice. Email reminders to complete the sharing exercise will be provided. The sharing should be done in person, rather than via email or over the phone. The participant may choose with whom to share the pictures and may decide to show the same person his/her pictures each week for the 3 week period or may decide to share with different people each week or some combination thereof. Scripts are provided to guide the participants (see Appendix B). Given that the participants may have taken many more than the required photographs during the prior week for this project, the time it takes to share them will vary. However, participants will be asked to limit the interaction to approximately 15 minutes. Participants in the Picture This! group and the Document This! control group are not asked to share their photographs. Following the sharing activity, participants in the Picture This! Plus Social Sharing Group are asked to answer 5 questions online, again following a link they will have received by email (see Appendix E). To keep payment equal, all other participants are also asked to complete a weekly survey of 5 questions about taking and sharing photographs.

At the completion of the 3rd 7 day period, all participants will be invited back into the laboratory to complete an exit questionnaire packet and to repeat the 2 computerized tasks they completed at baseline. This packet will include the following measures:

- 1) Demographics and Psychiatric History Follow-up
- 2) Modified Differential Emotion Scale (MDES)
- 3) Self-Other Four Immeasurables Scale
- 4) Ambiguous Situation (with 10 novel statements)
- 5) Santa Clara Brief Compassion Scale
- 6) Gratitude Questionnaire (GQ-6)
- 7) Cognitive Style Questionnaire Short Form (CSSF)
- 8) Beck Depression Inventory – II (BDI-II)
- 9) State-Trait Anxiety Inventory (STAI)
- 10) Savoring Beliefs Inventory (SBI)

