- 11) Carolina Empirically Derived Mindfulness Inventory (CEDMI)
- 12) Brief Satisfaction with Life Scale (BSWLS)
- 13) Rosenberg Self Esteem
- 14) Scale of Physical Symptoms
- 15) Pittsburgh Sleep Quality Inventory (PSQI)

- 16) Social Connectedness Scale (SCS)
- 17) MOS Social Support Scale (MOS)
- 18) Perceived Stress Scale (PSS)
- 19) Life Events Scale (LES) Respondents will be asked to consider the time that has elapsed since baseline (which should be approximately 4-5 weeks).
- 20) Emotion Regulation Questionnaire (ERQ)
- 21) TOSCA-3 with 16 novel scenarios
- 22) Irritability Question
- 23) Intervention Assessment – 5 questions created by the project staff to assess participant satisfaction with prescribed exercises and to elicit suggestions for improvement.

The following compensation/incentive schedule for completing questionnaires and participating in the study will be utilized:

- Participants who complete the baseline questionnaire packet and computer tasks will be compensated \$10 or be provided with class credit via the psychology subject pool.
- Participants who complete the exit questionnaire packet and computer tasks will be compensated \$19 or be provided with class credit via the psychology subject pool.
- Participants will be compensated \$1/day for completing the nightly online questions for a potential total of \$21.
- Participants will be compensated \$1/each weekly survey completed for a potential total of \$3.

Hypothesized Outcomes

H1: Participants in the Picture This! (PT) and Picture This! Plus Social Sharing (PTPSS) conditions will evidence increased well-being as indexed by measures of: a) depressive symptoms, b) positive affect, c) savoring beliefs, d) mindfulness e) life satisfaction, f) self esteem, g) gratitude, h) physical health and sleep quality, and i) perceived social support, relative to participants in the active control and no picture control conditions.

H2: Participants in the Pictures This! Plus Social Sharing will demonstrate greater improvement in perception of social support than those in any other condition.

Mediators of Change.

H3: Participants in the PT and PTPSS conditions will show significant changes in automatic cognitive processes including attentional biases, interpretational biases, and cognitive style assessed via behavioral tasks and self report.

H4: Changes in the aforementioned cognitive processes will account for the positive changes in mental and physical health.

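### Enrolled students are not excluded as sharing partners, which leaves a small, avoidable route of contamination, mainly affecting H2

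*Combined protocol and SAP*

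**What the plan says.** **Recruitment and allocation.** Section 2 (Identification of Subjects) gives the sample: "Approximately 240 potential participants will be recruited at Clark University", with other local universities added where they agree. Channels include flyers on and off campus, email, and "in-class announcements, electronic advertisement boards and via the Clark psychology subject pool". The opening section describes students "who will be randomly assigned to 1 of 4 conditions". The unit is the individual student; no allocation ratio is given.

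**The sharing exercise.** Under 3. Testing Procedure, at the end of each of the three weeks, sharing-arm participants "are asked to share their photographs with a friend, relative, or loved one of their choice". On repeat partners: "The participant may choose with whom to share the pictures and may decide to show the same person his/her pictures each week"; different people in different weeks are also allowed. Sharing is face to face, guided by the Appendix B scripts, and kept to about 15 minutes. The Picture This! and Document This! arms are not asked to share, but are not asked to refrain either.

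**Measurement.** All four arms complete a weekly survey (Appendix F) on whether they shared their own pictures. As described, it does not ask whether the respondent was shown another participant's pictures.

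**Hypotheses.** H2 states that the sharing arm "will demonstrate greater improvement in perception of social support than those in any other condition". H1 compares Picture This! and the sharing arm together with the two control arms, and perceived social support is one of its outcomes. The analysis paragraphs have no provision for exposure across arms.

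**The concern.** Friends, classmates and housemates can enrol through the same channels and be randomised to different arms. A sharer may then pick one of them as the partner. The in-person requirement may favour people close at hand, including fellow students, though this is an inference.

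Such a partner has a friendly, scripted conversation built around positive photographs, and may learn what the savoring exercise involves, before completing the exit questionnaires. H2 is most directly exposed, because its outcome is perceived social support and the sharing session is itself a social contact. If the session benefits the partner, the comparator mean rises and the H2 contrast shrinks. H1 shrinks only where the partner is in Document This! or the passive control.

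Because the survey as described records outgoing sharing and not receipt, the trial could not say afterwards how often this happened. A null H2 would then be harder to interpret.

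**Working it through.** **The plan's own figure.** The only figure is about 240 participants. No alpha, power, effect size, SD, dropout or contamination allowance accompanies it, so it can be neither reproduced nor refuted. What follows only scales the problem.

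**Inputs**
- From the documents: 240 participants, four arms, three weekly sharing sessions, and the same or different partners.
- Assumed: equal allocation, so 240/4 = 60 per arm and 180 participants outside the sharing arm.
- Assumed: *p*, the chance that a chosen partner is enrolled in any arm, is 2% to 10%.
- Assumed: *f*, the share of the effect passed to a partner, lies between 0 and 1.
- *m*, the number of distinct partners per sharer, is 1 to 3.

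**Is 2-10% a reasonable range?** Under random mixing, *p* = 239/(pool size). An assumed pool of 10,000 students gives 2.4%, and one of 2,500 gives 9.6%. Friends enrolling together would raise *p*; relatives and off-campus friends would lower it.

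**Exposed comparators.** An enrolled partner is in another arm with probability 180/239 = 0.753. The expected number exposed is 60 × *m* × *p* × 0.753, and the exposed share *c* is that number divided by 180. Repeat exposure of one person is ignored.

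| Partners per sharer | *p* | Exposed | *c* |
|---|---|---|---|
| 1 | 2% | 60 × 0.02 × 0.753 = 0.9 | 0.5% |
| 1 | 10% | 60 × 0.10 × 0.753 = 4.5 | 2.5% |
| 3 | 2% | 180 × 0.02 × 0.753 = 2.7 | 1.5% |
| 3 | 10% | 180 × 0.10 × 0.753 = 13.6 | 7.5% |

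**Effect on a contrast.** With exposure spread evenly over the comparator arms, the expected difference is *d* × (1 − *c* × *f*). For scale, take 60 v 60, two-sided 5% and 80% power. The detectable difference is *d* = (1.960 + 0.842) × √(2/60) = 0.51, and power becomes Φ(2.802 × (1 − *cf*) − 1.960).

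- One partner, *p* = 10%, full transfer: *cf* = 0.025, power 78%.
- New partner weekly, *p* = 10%, full transfer: *cf* = 0.075; 2.802 × 0.925 − 1.960 = 0.632, power about 74%.
- The same with a quarter of the effect transferred: *cf* = 0.019; 2.802 × 0.981 − 1.960 = 0.789, power about 78%.

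Power falls below 75% only if *cf* exceeds 0.06, which within this range needs the top of the *p* range, a new partner nearly every week and most of the effect passing on.

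**Timing.** Exposure matters only between the partner's own baseline and exit, roughly 4-5 weeks. With staggered enrolment, some enrolled partners will be outside that window, so the exposed shares above lean high.

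**The case against.** The strongest reply is that the gap may not exist and would be minor if it did. The Appendix B scripts, Appendix C screen and Appendix F survey are not in the supplied text, and any of them could already restrict partner choice or ask about receipt. The 2-10% is an assumption, and the protocol's allowance for the same partner each week points to the lower rows of exposure. All of this stands, and it limits the point to a cheap improvement.

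A reader might infer more than the documents support:

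- *That partner choice is unrestricted.* It is not: the partner must be a friend, relative or loved one, seen in person.
- *That sharers deliver the intervention to controls.* The intervention is 21 days of noticing and photographing plus a nightly exercise. A partner looks at someone else's pictures for about 15 minutes, at most three times per sharer. For H1 outcomes, *f* is likely well below 1.
- *That exposing Picture This! participants dilutes H1.* That arm is on the experimental side of H1; its exposure bears on H2 only.
- *That H2 requires social contact to be unique to the sharing arm.* It predicts greater improvement, and H1 already predicts better perceived support in Picture This!.
- *That exposure runs one way.* Other arms may share informally, and the weekly survey anticipates this.
- *That the rule "Participants will not have access to other participants" (others' photographs) is contradicted.* That sentence concerns the upload drive and sits with the confidentiality text. Showing one's own pictures does not breach it.
- *That controls would otherwise not know of the active exercise.* Consent pages were removed and the protocol states there is no deceit, so this cannot be judged.

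**Conclusion.** The point holds as a minor design gap. The available text allows an enrolled comparator to be a sharing partner and does not describe any measurement of receipt. If exposure helps the partner, the bias runs toward the null, on H2 directly and on H1 only through the two control arms. Dilution of either hypothesis is not demonstrated. The exposed shares and power losses rest on equal allocation, an assumed partner rate and an assumed transfer fraction, none of which the documents give. Under most combinations the loss of power is about two points or less; the larger figure needs all the unfavourable assumptions together. The case for acting is that prevention is nearly free, and that exposure left unmeasured cannot be quantified later.

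**What to change.** 1. In the sharing paragraph of 3. Testing Procedure and in the Appendix B script, ask sharing-arm participants to choose someone who, as far as they know, is not taking part in the study. Skip this if Appendix B already says so.
2. Add one item to the weekly survey in all four arms: whether, in the past week, the respondent was shown photographs that another participant took for this study. Report the answers descriptively by arm, and keep the primary analysis as randomised. Removing exposed participants after randomisation could itself introduce bias.

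**Cost.** One sentence and one survey item, with no change to the sample size. Sharers have a slightly narrower choice of partner, and both changes may prompt some talk about who is taking part. Screening applicants about enrolled housemates, or deferring their enrolment, is not recommended: it asks people to disclose someone else's participation and slows recruitment for little gain.
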